2. STUDY OBJECTIVES AND ENDPOINTS

2.1. Objectives

2.1.1. Primary Objective

The primary objective of this study is to:

- Investigate the efficacy of imlifidase compared with PE in removal of DSA in patients who are experiencing an active or chronic active AMR episode after kidney transplantation

2.1.2. Secondary Objectives

Secondary objectives of this study are to:

- Evaluate DSA levels up to 180 days after treatment
- Evaluate HLA-antibodies levels up to 180 days after treatment
- Evaluate the overall kidney function up to 180 days after treatment
- Investigate the occurrence of AMR up to 180 days after treatment
- Investigate the safety and tolerability of imlifidase compared to PE in patients experiencing active or chronic active AMR episodes
- Evaluate the number of PE-sessions needed
- Evaluate the pharmacokinetics, pharmacodynamics and immunogenicity of imlifidase

2.2. Endpoints

2.2.1. Primary Endpoint

The primary endpoint of this study is:

- Maximum reduction in mean DSA level at any time point during the 5 days following the start of treatment

2.2.2. Secondary Endpoints

Secondary endpoints of this study are:

- DSA levels up to 180 days after treatment
- HLA-antibodies levels up to 180 days after treatment
- Kidney function change from baseline (at screening) as evaluated by eGFR, P-creatinine and albumin/creatinine ratio in urine up to 180 days after treatment
- Proportion of subjects with graft loss within 180 days of treatment
- Signs of transplant glomerulopathy 180 days post treatment
- Change from baseline (at screening) in histopathology per Banff Criteria at 29 and 180 days

- Change from baseline (at screening) in mRNA levels in kidney biopsies evaluated by [REDACTED] at 29 and 180 days from baseline. If kidney biopsy is performed before screening, mRNA levels will be evaluated on day 29 and day 180 (no baseline will be available)
- Safety parameters (AEs, safety laboratory tests, vital signs and ECG)
- Type, frequency and intensity of adverse events
- Number of sessions with PE
- Total Serum IgG levels over time
- Presence of intact IgG on SDS-page/Western blot until start of IVIg treatment
- DSA functionality determined by C1q or C3d analysis pre- and post-treatment
- PK profile of imlifidase (C_{max} , T_{max} , $t_{1/2}$, AUC, CL, V)
- Presence of ADA (anti-imlifidase IgG)

3. INVESTIGATIONAL PLAN

3.1. Overall Study Design

This is a randomized, open label, multi-centre, study with an active control. The study will primarily examine the reduction in mean levels of DSA after treatment with imlifidase compared to PE in patients diagnosed with active or chronic active AMR according to Banff 2017 criteria (Haas et al. 2018), including presence of DSA(s). A total of 30 male and/or female patients will be included in the study.

The randomization will be 2:1. 20 subjects will receive a single dose of 0.25 mg/kg imlifidase and 10 subjects will be treated with 5-10 sessions of PEs. High dose IVIg followed by a single dose of rituximab will be given after treatments with imlifidase and PE. For doses, see Section 5. Other treatments and/or procedures for AMR can be used as required at the investigator’s discretion. SOC treatment can be initiated at any point for patients in the treatment arm if needed as judged by the investigator. The decision to initiate other SOC treatments will normally be based on DSA rebound. Since DSA is monitored frequently, signs of antibody rebound will be detected early and appropriate treatment initiated immediately.

The duration of the hospitalization for subjects in the imlifidase arm will be at least 2 days. In the control arm, the duration of the hospital stay will follow standard of care at each study site.

Presence of DSA will be assessed pre-dose and at multiple times during the study. Protocol biopsies will be performed at screening, and on day 29 and day 180 after first day of treatment to assess changes in allograft histopathology and mRNA levels. . If kidney biopsy is performed within 5 days prior to screening it will not have to be repeated at screening visit and mRNA levels will be measured on day 29 and day 180. In addition, kidney function will be followed by plasma or serum creatinine measurements, eGFR calculations and albumin/creatinine ratio in urine during the full study period.

The study outline is summarized in Figure 1 (imlifidase) and Figure 2 (PE) below.

Figure 1: Overall study outline imlifidase arm

[figure not shown]
[figure not shown]

Figure 2: Overall study outline PE arm

Safety parameters (safety laboratory tests, vital signs and ECG) as well as kidney function and AEs will be monitored up to 180 days after start of treatment.

3.1.1. Follow-up Procedures

The subjects will be followed until 180 days after start of treatment. Subjects who lose their graft during the course of the study will remain in the study and be followed according to the study protocol and clinical practice at the site.

After study completion, all study subjects will be followed regularly by the nephrologist or transplant surgeons according to each centre's follow-up routines for transplanted subjects. The frequency of outpatient visits will be adjusted individually to the state of patient health and transplant function.

3.1.2. Safety Review Committee

A Safety Review Committee (SRC) will be established to evaluate safety and tolerability data. The committee will meet 14 days after the first patient has received the first treatment to evaluate available safety and tolerability data. If no clinically significant changes are identified, the second and third subject will be dosed and evaluated following the same schedule. After 6 and 11 imlifidase-treated subjects have completed visit 8 (day 29) the committee will meet again. Evaluation of data will include subjects from both treatment arms (i.e., imlifidase and PE). The SRC will meet on an ad hoc basis if any important safety issue arises anytime during the conduct of the study. The SRC will consist of at least 3 physician members: a drug safety physician, and two consultants, all independent to Hansa Biopharma. Other internal and external experts will be invited to attend the meetings if any issue arises that require additional expertise. A working procedure for the SRC will be described in an SRC charter.

3.2. Study timeline

The expected study start is Q1 2019 with 12 months recruitment and 6 months follow up for included subjects. The recruitment period has been extended to 35 months.

3.3. Planned number of study sites and subjects

This is a multi-centre study. Approximately 14 sites, in US, Europe and Australia, will be included. A total of 30 male and/or female subjects will be enrolled in the study.

3.4. End-of-Study

The planned end-of-study is defined as last subject last visit. Hansa Biopharma will ensure that an end-of-study notification is submitted to the concerned Regulatory Authority (RA) and Independent Ethics Committee (IEC)/Institutional Review Board (IRB) according to local requirements.

For procedures in case of premature termination or suspension of the Study, see [Section 13.4](#).

4. STUDY POPULATION

4.1. Selection Criteria

To be eligible for the study, subjects must meet all inclusion criteria and no exclusion criteria. If a subject has been screened and meets all inclusion and no exclusion criteria but does not receive imlifidase and a new AMR occurs, the subject may be rescreened.

4.2. Inclusion Criteria

1. Signed Informed Consent obtained before any study-related procedures
2. Willingness and ability to comply with the protocol
3. Male and/or female donor kidney recipients age ≥ 18 years at the time of screening
4. Presence of DSA(s)
5. Meet the Banff 2017 criteria for active or chronic active AMR
6. At least 25% rise in serum creatinine compared to last individual value taken prior to the AMR. Patients with delayed graft function and AMR within 10 days after transplant (confirmed by kidney biopsy) can be included regardless of serum creatinine level
7. Women of child-bearing potential willing or able to use at least one highly effective contraceptive method throughout the study. In the context of this study, an effective method is defined as those which result in low failure rate (i.e. less than 1% per year) when used consistently and correctly such as:
 - combined (estrogen and progestogen containing) hormonal contraception associated with inhibition of ovulation
 - oral
 - intravaginal
 - transdermal
 - progestogen-only hormonal contraception associated with inhibition of ovulation
 - oral
 - injectable
 - implantable
 - intrauterine device (IUD)
 - intrauterine hormone-releasing system (IUS)
 - bilateral tubal occlusion
 - vasectomised partner
 - true abstinence: When this is in line with the preferred and usual lifestyle of the subject. [Periodic abstinence (such as calendar, ovulation, symptothermal, post-ovulation methods) and withdrawal are not acceptable methods of contraception]
8. Men willing to use double-barrier contraception from the first day of treatment until at least 2 months after the dose of imlifidase, if not abstinent

4.3. Exclusion Criteria

1. Previous treatment with imlifidase
2. Previous high dose IVIg treatment (2 g/kg) within 28 days prior to inclusion
3. Lactating or pregnant females
4. Significantly abnormal general serum screening lab results judged inappropriate for inclusion in the study by the investigator
5. Intake of other investigational drugs within 5 half-lives (or similar) of the product prior to inclusion
6. Clinically relevant active infection(s) as judged by the investigator
7. Any condition that in the opinion of the investigator could increase the subject's risk by participating in the study such as severe immune deficiency and severe cardiac insufficiency (New York Heart Association (NYHA) Class IV) or severe uncontrolled heart disease
8. Known allergy/sensitivity to imlifidase, IVIg and/or rituximab and the respective excipients
9. Patient unable to tolerate treatment with plasmapheresis or immunoadsorption, as judged by the investigator
10. Unsuitable to participate in the study for any other reason as judged by the investigator
11. Positive PCR test for SARS-CoV-2 virus infection.
12. Current diagnosis or history of thrombotic thrombocytopenic purpura (TTP), or known familial history of TTP

4.4. Method of Assigning Subjects to Treatment Groups

At the screening visit, study subjects will be identified by a site-specific screening identification number. The lowest available site-specific subject number will be allocated, when the subject has fulfilled the eligibility criteria. The subjects will be randomized to imlifidase or PE treatment in a 2:1 ratio according to a computer-generated randomisation list created by the CRO. Block randomisation will be used.

4.5. Discontinuation of Subjects

The subjects have the right to withdraw from the study at any time for any reason, without the need to justify their decision. However, the investigator should record the reason for the subject's withdrawal, if possible. The investigator also has the right to withdraw subjects. In either event, the investigator must notify monitor.

A subject that prematurely discontinues participation must, if possible, be called in for a last visit and undergo the assessments and procedures scheduled for the end of study follow up visit. Even if the subject is not able to attend, the End of Trial Form in the eCRF must be completed. Subjects who, for a medical reason, cannot comply with the protocol procedures will be followed by best procedure to retrieve safety and efficacy data.

Minor infusion-related reactions have been observed in some patients receiving imlifidase for other indications. These are usually mild and include chest discomfort, flushing, pharyngeal oedema and dyspnea. More severe reactions can occur.

If a minor infusion-related reaction (CTCAE grade 1 or 2) is suspected the infusion should be temporarily stopped and the patient should be observed for clinical signs of allergic reactions. If a significant infusion-related reaction or anaphylactic reaction occurs (CTCAE grade 3 or higher) then the imlifidase therapy should be discontinued immediately.

The patient should be treated by the investigator according to local practice for an allergic reaction or a severe allergic reaction/anaphylaxis, respectively. If the symptoms resolve, the infusion can be resumed. If the symptoms persist or worsen then the drug infusion should not be restarted.

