As for all biologics, there is a risk of infusion reactions associated with imlifidase treatment. Three non-serious and one serious infusion related reactions regarded as related to treatment have occurred in 114 subjects receiving imlifidase. Signs and symptoms associated with infusion related reactions included, but were not limited to dyspnoea, pharyngeal oedema, sinus tachycardia, chest discomfort and flushing. To mitigate the risk of infusion related reactions, all subjects receive glucocorticoid and antihistamine treatment prior to dosing and are closely monitored during the infusions.

In vitro studies have revealed that imlifidase cleaves biologics originating from rabbit and human IgG including; thymoglobulin, IVIg, basiliximab, alemtuzumab, rituximab, adalimumab, denosumab, belatacept and etanercept. The optimal interval between imlifidase administration and these biologics has not been tested (2018-003R).

The rationale for the 3-day window between imlifidase and IVIg dosing is aimed to prevent cleavage of the IVIg based on the pharmacokinetic and pharmacodynamic profiles of imlifidase. In one of the clinical studies (14-HMedIdeS-04), alemtuzumab was given four days post dosing of imlifidase and in one clinical study (15-HMedIdeS-06), IVIg was given seven days post dosing of imlifidase.

Adverse events after administration of IVIg do occur but are seldom serious. There is a very small risk of anaphylaxis, often in subjects with severe IgA deficiency. Other reported side effects include headache, myalgia, transient hypotension and flushing (all of which can be corrected by slowing the infusion rate), meningism, aseptic meningitis, skin reactions (especially eczema), neutropenia, worsening of renal failure, and thromboembolic events (DVT, MI and stroke) attributable to hyperviscosity ([Hughes et al. 2014](#)).

As an extra safety measure for women of child bearing potential, the requirement for highly effective contraception is part of the inclusion criteria for this study. Additionally, a pregnancy test will be performed at the screening visit to ensure the patient is not pregnant.

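### Protocol 4.5 lets the infusion be resumed once symptoms resolve without naming a CTCAE grade, which read literally conflicts with its own order to discontinue imlifidase for grade 3 or higher

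*Protocol*

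**What the plan says.** Protocol 4.5 deals with infusion reactions in two consecutive paragraphs.

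The first sets two tiers by grade. For the lower tier, "If a minor infusion-related reaction (CTCAE grade 1 or 2) is suspected the infusion should be temporarily stopped" and the patient is observed. For the upper tier, which joins significant infusion reactions with anaphylaxis, the text reads "anaphylactic reaction occurs (CTCAE grade 3 or higher) then the imlifidase therapy should be discontinued immediately".

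The second paragraph opens with treatment for both tiers, "treated by the investigator according to local practice for an allergic reaction or a severe allergic reaction/anaphylaxis, respectively". Two sentences on restarting follow directly: "If the symptoms resolve, the infusion can be resumed" and "If the symptoms persist or worsen then the drug infusion should not be restarted". Neither mentions a grade.

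Protocol 1.3 gives the only frequency figure: "Three non-serious and one serious infusion related reactions regarded as related to treatment have occurred in 114 subjects receiving imlifidase". It also describes premedication and monitoring, but says nothing about when an interrupted infusion may be restarted.

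**The concern.** The discontinuation order is tied to grade 3 or higher. The permission to resume is tied only to resolution of symptoms, and it sits in a paragraph that has just named severe allergic reaction and anaphylaxis. A severe reaction that resolves therefore meets the literal condition of both sentences, and they point in opposite directions.

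This is an instruction to be followed at the bedside, within a 15-minute infusion, at approximately 14 sites (Protocol 3.3 and 5.1). Staff should not have to infer which reactions the permission covers. At stake is how an individual patient with a severe reaction is handled.

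**Working it through.** The protocol states no figure on this point, so the main check is a comparison of the sentences. A short calculation then gauges how often the situation might arise.

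**Step 1. The sentences of Protocol 4.5 in order.**

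1. Grade 1 or 2: pause and observe. Grade named.
2. Grade 3 or higher, or anaphylaxis: discontinue at once. Grade named.
3. Treat by local practice, "for an allergic reaction or a severe allergic reaction/anaphylaxis, respectively". Both tiers are in scope.
4. Symptoms resolve: the infusion may go on. No grade named.
5. Symptoms persist or worsen: no restart. No grade named.

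For a grade 1 or 2 reaction that resolves, sentences 1 and 4 agree. For a grade 3 or higher reaction that does not resolve, sentences 2 and 5 agree. For a grade 3 or higher reaction that does resolve, sentence 2 says discontinue and sentence 4, taken as written, says the infusion may resume. The conflict lies only in that last case.

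**Step 2. Does other text settle the scope?**

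- Protocol 1.3 gives frequency, typical signs, premedication and monitoring, but no restart rule. The end of 1.3 refers to the Investigator's Brochure for guidance.
- Protocol 4.3 excludes known allergy or sensitivity to imlifidase, but only at entry.
- Protocol 5.1 covers preparation and the single infusion, and refers to a pharmacy manual for details.
- The SAP says nothing on restarting an infusion.

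The Investigator's Brochure and pharmacy manual are not among the documents, so they can be assumed neither to resolve the point nor to leave it open.

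**Step 3. Do the described symptoms separate the tiers?** No. Protocol 4.5 lists dyspnoea and pharyngeal oedema among reactions that are usually mild. Protocol 1.3 lists the same signs for a set of reactions that includes the serious one. The CTCAE grade is the only divider the text offers, and sentences 4 and 5 omit it.

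**Step 4. Size.** Inputs: 3 non-serious and 1 serious related reactions in 114 subjects (Protocol 1.3); 20 planned imlifidase patients (Protocol 3.1).

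- Serious reactions: 1/114 = 0.9%. Expected among 20: 20 × 1/114 = 0.18.
- Chance of at least one serious reaction among 20: 1 − (113/114)^20 = 0.16.
- All related reactions: 4/114 = 3.5%. Expected among 20: 20 × 4/114 = 0.70.

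Only grade 3 or higher reactions are in dispute, and the documents do not grade the four. If k of the four were grade 3 or higher, the expected number is 20k/114: 0 for k = 0, 0.18 for k = 1, and 0.70 only if all four were. Taking the one serious reaction as the proxy gives 0.18.

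**The case against.** The strongest reply is that the paragraphs have a coherent reading and the wording favours it. The lower tier is paused and the upper tier discontinued, and what is naturally resumed is what was paused. The restart sentences speak of the infusion, as the grade 1 or 2 sentence does, while the grade 3 sentence speaks of the therapy. If resumption also covered the upper tier, both tiers would follow the same course and the distinction drawn in the first paragraph would do no work. The word respectively keeps the two classes apart, and a permissive sentence does not expressly override an unqualified order.

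Most of this stands as an account of probable intent. It does not remove the defect, because the limit has to be inferred, and the sentence just before the permission names anaphylaxis.

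Three stronger readings are tempting, and the documents do not support them:

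- *That the protocol directs re-exposure after anaphylaxis.* It does not. The text leaves the scope of a permission unstated.
- *That sites would in fact act in opposite ways.* This cannot be shown without the Investigator's Brochure and pharmacy manual, which may give further instruction.
- *That uneven handling would distort the PK or DSA results.* This is speculative at the expected frequency. SAP 4.5 tabulates total dose and percentage of planned dose and lists planned and actual dose by patient. SAP 3.4 lets the PK analyst take deviations and non-compliance into account.

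**Conclusion.** The concern holds as a conflict on the literal reading: for a severe reaction that resolves, Protocol 4.5 permits in one paragraph what it rules out in the paragraph before. Limiting resumption to grade 1 or 2 is plausible and probably what was meant, but it is not stated, and no other supplied text states it.

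The situation is likely to be rare. About 0.18 serious reactions would be expected among 20 imlifidase patients, assuming that the past rate carries over and that seriousness stands in for grade 3 or higher. Both assumptions are weak: the rate rests on a single event, the earlier studies described in Protocol 1.1 used other doses and populations, and seriousness is not a CTCAE grade. The figure of 0.70 for all reactions should not be used as the size of this problem, since three of the four reactions were non-serious.

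Sample size, the primary analysis and error rates are unaffected. The case for changing the text rests on the possible consequence for one patient and on how little the change costs.

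**What to change.** Reconcile the two paragraphs of Protocol 4.5 so that the resumption sentence names the CTCAE grades it applies to and no longer conflicts with the discontinuation sentence. The sentence on not restarting should be given the same explicit scope. Which rule applies is for the sponsor's clinical team to decide, and none is proposed here.

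The sponsor should also check that the Investigator's Brochure, the pharmacy manual and the other country-specific protocols listed in SAP section 1 agree with the reconciled text.

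The cost is one clarified sentence, documented as an amendment under Protocol 13.1, and a notice to the sites. No analysis, table or sample size changes.

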5. STUDY TREATMENTS

5.1. Investigational Medicinal Product

Imlifidase is provided as a freeze-dried powder for concentrate for solution for infusion, 11 mg per vial. After reconstitution with sterile water for injection, the concentrate contains 10 mg/mL imlifidase. The concentrate will be added to 50 mL sodium chloride 9 mg/mL (0.9 %) solution for infusion and administered as an infusion.

The excipients are: mannitol, polysorbate 80, Tris (tris(hydroxymethyl)aminomethane) buffer and EDTA. The excipients are all of pharmacopoeial quality.

Imlifidase for infusion will be prepared by the pharmacist or study nurse and the administration will be performed by the study nurse or physician at site. Details on preparation, labelling, administration and accountability of imlifidase are described in the pharmacy manual that will be provided to the site and pharmacy prior to inclusion of the first subject.

One intravenous dose of imlifidase, 0.25 mg/kg, administered over 15 minutes, will be given to subjects randomized to receive imlifidase.

5.1.1. Conditions for Storage and Use

Vials with imlifidase should be stored in a refrigerator at +2°C to +8°C.

The solution for infusion should be stored at +2°C to +8°C, protected from light. The solution should be used within 12 hours. The solution should be placed in room temperature approximately 30 minutes before administration.

The investigator will ensure that the Investigational Medicinal Product (IMP) always will be stored in appropriate conditions in a secure location. The storage compartment will be monitored regularly, and the temperature documented.

